The pilot study consists of a two-arm, 16-week, open-label, randomized, pilot trial of XR-NTX vs. TAU for treatment of opioid and alcohol use disorders in HIV-infected patients. Study participants are individuals with HIV infection and alcohol and/or opioid use disorders and who have received patient-centered information about both antagonist and agonist treatment options for alcohol and opioid use disorders. During screening, eligible participants will be surveyed regarding their attitudes about opioid antagonist therapy for opioid and alcohol use disorders (Aim 2). We will track the rate of participant recruitment (i.e., no more than 50 participants over no more than 12 months) to estimate duration of study recruitment required for a multisite study (Aim 3). Eligible patients are randomized in a 1:1 ratio to receive XR-NTX vs. TAU (Aim 4). Participants with both alcohol and opioid use disorders will be categorized by their self-reported substance of choice. XR-NTX (provided as Vivitrol®) will be administered by HIV clinic providers as a monthly intramuscular injection. Study visits will occur every 4 weeks for collection of blood and urine samples, safety, and other assessments. Primary outcomes of treatment initiation within 4 weeks of randomization, and retention at 16 weeks (maximum of 4 XR-NTX injections) and analyzed by intent-to-treat will be assessed. Secondary outcomes assessed at 16 weeks include change in 1) HIV-1 RNA viral suppression, 2) illicit drug and alcohol use, 3) HIV care engagement (receipt of ART, HIV visit adherence, ART adherence), and safety (percent with precipitated withdrawal, overdose, transaminitis).

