- 5) Retention on treatment (Aim 4B): Retention on treatment is defined as the percent of assigned treatment received over 16 weeks after treatment initiation. Only participants who initiate treatment (as defined in Aim 4A) will be assessed for retention on treatment. Retention will be assessed by the study clinician at 4, 8, 12, and 16 weeks following treatment initiation. For those randomized to XR-NTX, retention on treatment is defined as the mean percent of expected XR-NTX doses received (25%, 50%, 75%, or 100% of 4 possible doses). For those randomized to TAU, study clinicians will estimate the percent of recommended treatment a participant received in the past 4 weeks at weeks 4, 8, 12, and 16. Retention on treatment for TAU is defined as the mean percent of recommended TAU treatment received (1-100% possible range), as estimated by the study clinician (percent; chart review and self-report).

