- 5) Retention on treatment (Aim 4B): Retention on treatment is defined as the percent of assigned treatment received over 16 weeks after randomization. Only participants who initiate treatment (as defined in Aim 4A) will be assessed for retention on treatment. Retention will be assessed by the study clinician at 4, 8, 12, and 16 weeks following treatment initiation. For those randomized to XR-NTX, retention on treatment is defined as the mean percent of expected XR-NTX doses received (25%, 50%, 75%, or 100% of 4 possible doses). For those randomized to TAU, study clinicians will estimate the percent of recommended treatment a participant received in the past 4 weeks at weeks 4, 8, 12, and 16. Retention on treatment for TAU is defined as the mean percent of recommended TAU treatment received (1-100% possible range), as estimated by the study clinician. (percent; chart review and self-report).

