The proposal for a phase III randomized trial assumes enrollment of 400 participants from 8 sites in 18 months, implying a recruitment rate of about 2.28 participants per site-month. **Table 17.2.1** explores by simulation the consequences for the precision of various pilot-study-derived estimates of having a pilot study in which per site-month recruitment rate = (1.14, 2.28), number of sites = (1,2), and time period = (12 months, 18 months). **Table 17.2.1** investigates limiting the pilot sample size to 50 participants (n-limited), or limiting the enrollment time to 12 or 18 months (t-limited), or limiting both sample size and recruitment time simultaneously (n- and t-limited). The columns of **Table 17.2.1** headed – “Parameters” depict all the parameter combinations investigated.

5) The notation used in **Table 17.2.1** follows:

- n = pilot study sample size
- t = pilot study recruitment time (months)
- s = number of sites in the pilot study
- rate = recruitment rate (participants per site-month) assumed for both the pilot study and the subsequent phase III randomized trial
- N = randomized trial sample size (assumed to be 400)
- T = randomized trial recruitment time (months). This assumes that the sites in the randomized trial will exhibit the same performance that they did in the pilot study.
- S = number of sites in the randomized trial (this is not actually shown in **Table 17.2.1**, but is assumed to be 8)
- $\hat{T} = \frac{s/n}{S/N} t$, the estimator, derived from the pilot study, of the recruitment time for the subsequent phase III randomized trial
- $p(\text{init})$ = the probability of treatment initiation, which is the chance that a participant who is randomized to one of the two arms within the pilot study will obtain the 1st dose of the treatment. There is one $p(\text{init})$ calculated for each of the two arms.
- $p(\text{ret})$ = the probability of retention, which is the chance that a pilot-study participant who has obtained the 1st dose will still be on treatment at 4 months. There is one $p(\text{ret})$ calculated for each of the two arms.

6) The columns of **Table 17.2.1** headed “Outcomes (Percentiles)” show the consequences for various outcomes, given the parameters controlling the pilot study. Their meanings follow:

- 20% n = the 20th percentile of the sample size of the pilot study. The pilot study will very likely recruit at least this many participants

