17.3 Analysis of Randomized Pilot Study Primary Outcomes

The probability of treatment initiation (Aim 4A) and the probability of retention on treatment (Aim 4B), which are calculated separately for the two arms, are both based on ordinary (conditional) binomial samples, and will be estimated using maximum likelihood techniques, with exact binomial confidence intervals. We do not contemplate a multiplicity adjustment.

The rate of participant recruitment into the trial (Aim 3) can be estimated simply using maximum likelihood assuming an underlying Poisson process, but we feel it is more meaningful and useful for planning to predict the time required for recruitment in a subsequent randomized trial with 400 participants coming from 8 sites. We will do this via a bootstrap simulation. In each iteration of the simulation, the steps will be as follows:

- Draw a bootstrap sample of 8 sites from the 2 pilot-study sites.
- For each site, draw a bootstrap sample of, say, 1000 inter-arrival times from the inter-arrival times for that site to get 1000 simulated enrollment times (starting from time 0) for the site. Note that we consider that the time between the last enrollment at that site and the 12 month time point is also an inter-arrival time for that site. We will use this inter-arrival time in the simulation, but will not associate it with a simulated enrollment¹.
- Treating the 8 bootstrapped sites as simultaneously enrolling, determine T, the time of enrollment of the 400th patient in the simulated trial.

Repeating this iteration 10,000 times will generate 10,000 T-values that will constitute a predictive distribution for the enrollment times in the subsequent randomized trial. It is necessary to assume that the sites in the pilot study are a representative sample of the sites that will participate in the subsequent randomized trial.

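### Aim 4B retention is defined as a percent among initiators but analysed as a yes/no probability, and the between-arm contrast promised for it would not compare the randomized groups

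*Protocol*

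**What the plan says.** **Definition.** Sections 8.1 and 17.1 both make retention a percent. For XR-NTX it is the "mean percent of expected XR-NTX doses received (25%, 50%, 75%, or 100% of 4 possible doses". For TAU it is the "mean percent of recommended TAU treatment received (1-100% possible range), as estimated by the study clinician". The population is restricted: "Only participants who initiate treatment (as defined in Aim 4A) will be assessed for retention on treatment".

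**Time origin.** Section 17.1: "Retention on treatment is defined as the percent of assigned treatment received over 16 weeks after randomization". Section 8.1: "Retention on treatment is defined as the percent of assigned treatment received over 16 weeks after treatment initiation". Objective 4B in 5.1 also counts from initiation, and so does the visit timing given later in the same 17.1 item.

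**Analysis.** Section 17.3 works with a probability of retention, calculated separately by arm. It says the samples for initiation and retention "are both based on ordinary (conditional) binomial samples, and will be estimated using maximum likelihood techniques, with exact binomial confidence intervals". The notation for Table 17.2.1 describes p(ret) as "the chance that a pilot-study participant who has obtained the 1st dose will still be on treatment at 4 months".

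**Comparison.** Objective 4B in 5.1 is to compare the arms, and Aim 4 Pilot Objective A in 2.1 asks for effect size estimates, XR-NTX vs TAU. Section 6.1 states: "retention at 16 weeks (maximum of 4 XR-NTX injections) and analyzed by intent-to-treat will be assessed". Section 17.6 uses intent-to-treat only in the sense that participants stay in the arm to which they were randomized.

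**The concern.** A primary outcome has two definitions that cannot both feed the stated analysis. A mean of individual percents is not a count of successes, so exact binomial limits do not apply to it. A yes/no status suits the method, but 8.1 and 17.1 do not define one. In an open-label trial this leaves the choice of outcome until after the data have been seen. The retention figure is also a planning input for a 400-participant trial.

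The second issue is who is compared. Starting XR-NTX requires detoxification where needed, a urine screen negative for opioids and, after recent opioid use, a negative naloxone challenge (9.3.3.1, 9.3.3.2). Starting TAU can mean one day at a 12-step group (8.1). Initiators in the two arms may therefore be differently selected, so a difference between them is not protected by randomization.

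**Working it through.** **1. The plan's own precision figure.** Inputs from 17.2: 2.28 participants per site-month, 2 sites, 12 months, a cap of 50, 10% lost before initiation, and a 95% interval. Allocation is 1:1 (6.1). The document gives no true probability, so values from 0.5 to 0.8 were tried.

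- Simulated total: N = min(Poisson(2.28 × 2 × 12 = 54.72), 50), half per arm; initiators are binomial with probability 0.90.
- Exact interval for x of n: lower limit = Beta quantile (0.025; x, n − x + 1), upper limit = Beta quantile (0.975; x + 1, n − x). The half-width is half the distance between them.

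| 80th percentile of half-width | p(init) | p(ret) |
|---|---|---|
| Table 17.2.1 | 0.21 | 0.22 |
| Recomputed, true probability 0.5 | 0.206 | 0.223 |
| Recomputed, true probability 0.6 | 0.204 | 0.221 |
| Recomputed, true probability 0.8 | 0.187 | 0.198 |

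The published figures come back when each initiator is scored yes or no. The precision argument therefore rests on the binary outcome, not on the percent in 8.1 and 17.1.

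**2. What the missing rule does to the result.** Assume 22 XR-NTX initiators, of whom 10, 5, 4 and 3 received 4, 3, 2 and 1 doses.

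- Mean percent: (10 × 100 + 5 × 75 + 4 × 50 + 3 × 25) / 22 = 1650 / 22 = 75%. SD 0.278, standard error 0.278 / √22 = 0.0593, half-width 2.08 × 0.0593 = 0.12.
- All four doses: 10 / 22 = 45%, exact half-width 0.22.
- At least three doses: 15 / 22 = 68%, exact half-width 0.21.

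The same data give 75%, 45% or 68%, depending on a rule that the protocol does not state. For TAU there is no rule either for when an estimated percent means still on treatment.

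**3. Time origin.** Section 9.2.8 allows up to 4 weeks from randomization to initiation. For a participant who starts at week 4, the last retention assessment falls at 4 + 16 = 20 weeks after randomization, outside a 16-week window counted from randomization.

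**4. Conditioning on initiation.** Retention among all randomized = P(initiate) × P(retained given initiation). The rates below are assumed.

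| Initiation, XR-NTX vs TAU | Retention among initiators, both arms | Conditional difference | Retention among all randomized | Difference |
|---|---|---|---|---|
| 60% vs 95% | 60% | 0 | 36% vs 57% | −21 points |
| 70% vs 95% | 70% | 0 | 49% vs 66.5% | −17.5 points |
| 90% vs 90% | 60% | 0 | 54% vs 54% | 0 |

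**5. Precision after the change.** Over all possible results, the largest exact half-width per arm is 0.204 with 25 and 0.209 with 24. Among initiators only it is 0.218 with 22 and 0.223 with 21. The largest Newcombe half-width for the risk difference is 0.258 with 25 per arm and 0.263 with 24.

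**The case against.** The strongest reply is that a usable binary definition exists in the Table 17.2.1 notation, that 17.3 estimates that quantity, and that the precision figures agree with it. This stands in part. A reader might infer that the primary result cannot be computed at all; the documents do not support that. They support two competing definitions with no bridge between them.

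The conditioning is also disclosed. Section 17.3 says conditional and separate by arm, and 17.6 limits what intent-to-treat means. Initiation is itself a primary outcome, so all-randomized retention can be recovered by multiplication. The per-arm estimates are therefore sound if labelled conditional. The difficulty is confined to the comparison in 5.1, the effect size in 2.1 and the wording of 6.1.

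A reader might also infer that the unequal minimum scores (25% against 1%) bias the result towards XR-NTX. That is not shown. One injection is real exposure for about 28 days, and 1% is only the lowest estimate a clinician could give. If the binary version is used, the floors play no part; if the mean percent is used, the binomial interval does not apply. The two harms cannot both fall on one result.

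It is tempting to recompute precision with the 74% and 41% engagement rates cited in 4.1. Those concern clinic-based buprenorphine and methadone referral, not XR-NTX or TAU as defined here, so they are not used.

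Finally, the time-origin conflict may be a single misplaced word. It still needs correcting, because it sits in the definition of a primary outcome.

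**Conclusion.** The point holds as a conflict between stated rules on a primary outcome, and it should be fixed before analysis. The definition (percent, initiators) and the analysis (binary probability, exact binomial limits) do not match, and the planned half-width of 0.22 belongs to the binary version only. These findings, and the two time origins, rest on the text and need no assumed rates.

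The size of the selection problem does depend on assumptions. It is 21 points when initiation is 60% vs 95% with equal conditional retention of 60%, and it is nil if both arms initiate at the 90% that the protocol assumes. Even with equal initiation rates, the initiators in the two arms may differ in kind. No test or decision rule is attached to retention, so the consequence is a misleading planning estimate rather than a wrong formal conclusion.

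**What to change.** In 8.1, 17.1 and 17.3, use one binary definition: on assigned treatment at the end of the 16-week period, counted from one stated origin. Build it from the injection log for XR-NTX and from the TSR and Medication Assisted Treatment forms for TAU, with criteria of comparable stringency. For TAU, count only addiction treatment named in the participant's treatment plan, because 9.3.1 gives both arms usual-care counselling. Counting any single service would make TAU retention too easy to meet.

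For the between-arm comparison, include everyone randomized and count non-initiators as not retained. Report exact binomial intervals per arm (worst-case half-width about 0.20 to 0.21) and the risk difference with a Newcombe interval (worst case about 0.26). Keep p(ret) among initiators, labelled conditional, and the mean percent with a bootstrap interval, as supportive results. Correct the intent-to-treat wording in 6.1.

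The cost is wording; the treatment plan, injection log, TSR and medication forms are already in the schedule in 10.1. The downside is that headline retention will be lower, because non-initiators count as not retained.

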17.1 Primary Outcome Measures

Primary outcome variables for the CHOICES pilot study are:

- 1) HIV provider willingness to prescribe XR-NTX (Aim 1): HIV provider willingness to prescribe opioid antagonist treatment will be assessed with measures adapted from the Medical Opinion Survey (MOS) in the provider survey (mean; survey data).
- 2) Patient acceptance of opioid antagonist therapy (Aim 2): HIV-infected patient acceptance of opioid antagonist treatment will be assessed with measures adapted from the Medical Opinion Survey (MOS), administered during participant recruitment. Patients will be asked whether they are willing to participate in a trial of XR-NTX vs. TAU (binary; survey data).
- 3) Rate of participant recruitment into trial (Aim 3): Number of participants randomized in pilot study per 12 months. This will be used to estimate the speed at which a multisite trial could enroll participants. The number of participants randomized will be assessed on a monthly basis until either 50 participants have enrolled, or 12 months of recruitment have elapsed, whichever comes first (rate; randomization data).
- 4) Treatment initiation (Aim 4A): Treatment initiation is defined as receipt of at least one dose of study medication for those randomized to XR-NTX within 4 weeks of randomization. For those randomized to TAU, treatment initiation will be defined as receiving at least one dose of medication-assisted therapy other than XR-NTX (e.g., buprenorphine for opioid use disorder, disulfiram for alcohol use disorder), or attendance on at least 1 day of non-medication-assisted therapies (e.g., 12-step groups, outpatient rehab referral, etc.) within 4 weeks of randomization. Treatment initiation will be assessed with weekly phone calls from research staff until treatment is initiated or 4 weeks from date of randomization have elapsed, as which point a participant will be considered to have failed treatment initiation. (binary; chart review and self-report).

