17.2 Secondary Outcome Measures

1) HIV outcomes:

- a) HIV-1 RNA viral suppression (plasma HIV-1 RNA pcr \leq 200 copies/mL) at 16 weeks compared with screening (binary, laboratory assay).
- b) Change in CD4 count at the week 16 visit compared with screening (count; laboratory measurement).

2) Substance Use:

- a) Change in 30 day opioid abstinence (by Addiction Severity Index (ASI)-lite self-report, TLBF (self-report) and urine drug screen (UDS) confirmation) in the final 30 days of the 16 week trial compared to screening (binary; laboratory data and self-report).
- b) Change in past 30-day alcohol and other drug use by ASI-lite and UDS at week 16 visit compared to screening (binary; laboratory data and self-report).

3) Engagement in HIV Care:

- a) Change in the proportion of participants prescribed ART within 16 weeks following randomization, compared to baseline (binary; medical record abstraction).
- b) Proportion of participants taking 100% of prescribed ART doses in the past 3 days at 16 weeks for those prescribed ART at any point during the 16 week trial (proportion; self-reported ACTG adherence measure).
- c) Number of HIV primary care visits at 16 weeks (count, chart abstraction).

4) Participant safety:

- a) Change in liver enzymes between screening and week 16 visit (laboratory assay).
- b) Any fatal and non-fatal opioid overdose between screening and week 16 visit (binary; medical record abstraction and self-report).
- c) Change in Concise Health Risk Tracking score between screening and week 16 visit (continuous; self-report).
- d) Proportion of participants assigned to XR-NTX who develop precipitated opioid withdrawal.

Sample Size and Duration of Randomized Pilot Study Recruitment Phase

The randomized pilot study will recruit until either 50 participants have been enrolled or 12 months of recruitment have elapsed, whichever comes first. Justification for this decision follows:

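### The recruitment bootstrap in Section 17.3 runs each site's last interval to month 12 even if the pilot closes early at 50, so an early-closing pilot always predicts about 22 to 24 months for phase III.

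*Protocol*

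**What the plan says.** The stopping rule, under the sample size text in Section 17.2, is: "The randomized pilot study will recruit until either 50 participants have been enrolled or 12 months of recruitment have elapsed, whichever comes first". Sections 2.1 (Aim 3), 8.1 and 17.1 say the same.

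Section 17.3 prefers, over a simple Poisson rate, a bootstrap prediction of the time needed for a "subsequent randomized trial with 400 participants coming from 8 sites". The steps are:

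- "Draw a bootstrap sample of 8 sites from the 2 pilot-study sites".
- For each drawn site, resample its inter-arrival times. For this purpose "the time between the last enrollment at that site and the 12 month time point is also an inter-arrival time for that site", and "We will use this inter-arrival time in the simulation, but will not associate it with a simulated enrollment".
- Take the time of the 400th simulated enrollment, and repeat 10,000 times to obtain a predictive distribution.

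No exception is made for a pilot that closes before month 12. The footnote that justifies the final interval uses two examples, both of sites observed for a full year. The planning estimator in Section 17.2, by contrast, uses the pilot's actual recruitment time t.

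**The concern.** The footnote's reasoning is sound for a site that is open: waiting time without an enrollment is information and must not be discarded. It does not carry over to a site that has been closed because the study reached 50. From then on nobody could be enrolled, so the time says nothing about recruitment speed.

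The rule therefore fails when recruitment goes well. Once the cap is reached, the total number of enrollments (50) and the total time credited (2 sites × 12 months) are both fixed, so the average speed fed into the simulation no longer depends on how quickly the 50 arrived. Estimating that speed is the purpose of Aim 3, one of the pilot's primary outcomes.

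**Working it through.** **Inputs.** Cap of 50 participants, 12 months, 2 pilot sites; phase III of 400 participants at 8 sites, hence 50 per site (Sections 17.2 and 17.3). Two recruitment rates matter. Section 17.2 plans with 2.28, saying that the phase III proposal "assumes enrollment of 400 participants from 8 sites in 18 months", "implying a recruitment rate of about 2.28 participants per site-month". The stated target in fact gives 400/(8 × 18) = 2.78 per site-month; 2.28 would yield 2.28 × 8 × 18 = 328 participants. That mismatch is a separate matter, but both rates are used below. Arrivals are taken as Poisson.

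**Reproducing the plan's figures.** At 2.28, the 80th percentile of phase III recruitment time is the 0.8 quantile of a Gamma distribution with shape 400 and rate 8 × 2.28 = 18.24 per month. This is 22.85, and the table gives 23. The 20th percentile of pilot enrollment is that of Poisson(2 × 12 × 2.28 = 54.72), which is 48, as stated.

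**How often the pilot closes early.**

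- At 2.28: P(Poisson(54.72) ≥ 50) = 0.756.
- At 2.78: P(Poisson(66.67) ≥ 50) = 0.985.

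**What the rule does then.** Credited rate = 50/(2 × 12) = 2.083 per site-month. Predicted time = 400/(8 × 2.083) = 24.0 months. The month in which the 50th participant arrived does not appear.

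**Worked example.** Each site enrolls 25, evenly spaced, and recruitment closes at month 9. The true rate is 25/9 = 2.78, so 50 per site takes 18 months. Section 17.3 adds a 3-month interval without enrollment at each site, making 25 in 12 months. Run literally, the bootstrap gives a median of 23.9 months; with the interval ended at month 9 it gives 18.0. Closure at months 3, 6 and 11 gives medians of 21.4, 22.8 and 24.2 against true values of 6, 12 and 22. A 35/15 split between the sites changes little (21.5, 23.0 and 24.0 at months 3, 6 and 9).

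**Simulation.** Pilots were generated at a range of true rates, stopped at the earlier of 50 participants and 12 months, and passed through Section 17.3 as written (300 pilots per rate, 100 bootstrap iterations each). Median predicted months:

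| True rate per site-month | True phase III time | As written, pilots closing early | Interval ended at closing date, all pilots |
|---|---|---|---|
| 2.08 | 24.0 | 23.9 | 24.0 |
| 2.28 | 21.9 | 23.9 | 21.8 |
| 2.78 | 18.0 | 23.7 | 18.1 |
| 3.5 | 14.3 | 23.1 | 14.2 |
| 4.56 | 11.0 | 22.3 | 10.8 |
| 6 | 8.3 | 21.8 | 8.2 |
| 10 | 5.0 | 21.5 | 4.9 |

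Separate runs at 4.0 gave 22.6 to 22.9 months against a true 12.5. The overestimates are 23.9 − 21.9 = 2.0 months at 2.28, 23.7 − 18.0 = 5.7 at 2.78, and about 10 at 4.0.

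The last column covers all pilots because restricting to early closers selects those that happened to recruit fast. At 2.28 the corrected median among early closers alone is 21.0.

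**False precision.** At 2.78, the 10th to 90th percentile range of the predicted median across pilots is 23.0 to 24.1 as written and 14.7 to 21.3 after the correction. The written rule looks stable because it no longer responds to the data.

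**Where nothing goes wrong.** At 1.14 per site-month no simulated pilot reached the cap, and the written rule gives 44.8 against a true 43.9.

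**The case against.** The best defense is that the authors simply equated month 12 with the end of recruitment. The footnote speaks of waiting until the end of the trial, and the worked example in Section 17.2 expects recruitment to stop at 12 months. That is probably how the sentence arose. But the operative text names month 12, a programmer would implement it, and nothing elsewhere in the protocol corrects it.

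A second defense is that at the planning rate little is lost. This stands. At 2.28 the bias of about 2 months lies within the ±3 months that Section 17.2 accepts. Mean absolute error over all pilots is much the same either way (2.5 months as written, 2.4 corrected), and the prediction falls within 3 months of the true expected time more often as written (82% against 69%). The serious errors need about 2.78 or faster. That is above the rates in Table 17.2.1, but it is what the protocol's own phase III target requires.

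Four stronger readings are tempting and are not supported:

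- *That the result is about 24 months at any true speed.* Pilots that run to month 12 are predicted properly, and among early closers the value drifts down to between 21 and 22 months at very high speeds.
- *That the Aim 3 measure in Section 17.1 has the same fault.* Its wording, "Number of participants randomized in pilot study per 12 months", is labeled a rate and reads naturally as a unit. Section 2.1 says that recruitment time and number recruited will both be used.
- *That the rule could stop a feasible trial.* The protocol sets no go/no-go threshold on predicted recruitment time.
- *That poor coverage of the predictive interval shows the fault.* Coverage stays well below nominal after the correction too, so it cannot by itself be blamed on the month-12 end point.

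**Conclusion.** Wrong as written, and limited to Section 17.3. When 50 participants are reached before month 12, closed time is counted as time without recruitment, and the prediction is about 22 to 24 months whatever the sites' speed. Assuming Poisson arrivals at two sites with equal constant rates, this is the likely outcome: probability 0.76 at 2.28 per site-month and 0.99 at 2.78. The prediction is too long by about 2 months at 2.28, nearly 6 at 2.78 and about 10 at 4.0. The case at 2.78 matters most: sites recruiting just fast enough for the proposed 18-month phase III would be reported as needing nearly 24 months, an error about twice the stated tolerance. The 24-month arithmetic itself needs no Poisson assumption, as the evenly spaced and uneven-site examples show. Participants, randomization and the comparison of arms are untouched.

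**What to change.** In Section 17.3, replace the month-12 end point of each site's final interval with the date recruitment closed, defined as the date of the 50th randomization or month 12, whichever is first. This brings the analysis into line with the planning estimator in Section 17.2. The rest of the algorithm, including the rule that the final interval ends without an enrollment, can stay.

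Optionally, state in Section 17.1 that the Aim 3 rate is per site-month actually open. This is a clarification, not a correction.

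The cost is one phrase, or two sentences with the option. Randomization dates are collected anyway, so no new data and no change in conduct are needed.
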